## 12.2 Randomization and Enrollment

For the double-blind cohort, at Day 1 all eligible subjects will be randomized via IWRs to one of the three treatment arms (NGM282 3 mg, NGM282 6 mg, or placebo) in a 1:1:1 ratio. The proportion of subjects with diabetes (categorized on a dichotomous scale) will be balanced across the three groups to ensure an even distribution across the three groups.

Diabetes status for balancing (“no diabetes” or “diabetes”), will be based on medical history, Screening labs, current medications, and clinical assessments.

The single-blind cohort is not randomized. Subjects will initially be enrolled sequentially into dosing Group 1 and enrollment will be continuous within and between each dosing groups. Sequencing of the dosing Groups 2 and 3 will be based on PD and safety parameters from dosing Group 1 and may run in parallel to each other. A fourth optional dosing group may be conducted based on the safety/tolerability, imaging data and histology (dosing Group 3 only) data from the prior 3 dosing groups. Dosing Group 4 will be initiated only after all subjects in Cohort 3 have been enrolled and a minimum of 10 subjects have completed 12 weeks of treatment in order to do a preliminary review of key data. Dosing group sequence and individual subject treatment assignment will be blinded only study subjects throughout the study period.

For the placebo-controlled 24-week histology cohort, at Day 1 all eligible subjects will be randomized via IWRS to one of the two treatment arms (NGM282 1 mg or placebo) in a 2:1 ratio. The Sponsor, study sites, and subjects will be blinded to treatment assignment. The randomization schedule will be stratified by subject’s fibrosis stage 2 or 3 based on the screening qualification liver biopsy.

### **12.3 Test of Hypothesis and Significance Levels**

The null hypothesis being tested for this study will be that there is no difference in the absolute change in liver fat content from Baseline between the NGM282 and the Placebo treatment groups at EOT for the double-blind cohort. The alternative hypothesis being tested will be that there is at least a 5% difference in the absolute change in liver fat content from Baseline between the NGM282 and the Placebo treatment arms at Week 12 for the double-blind cohort. A two-sided analysis will be conducted at a 5% significance level.

Comparisons across the cohorts will be exploratory and further outlined in the SAP.

### **12.4 Study Populations**

The study populations are detailed below. Details of any other populations for analysis will be described in the SAP.

#### **12.4.1 Intent-to-Treat Population**

All randomized subjects in the double-blind and placebo-controlled 24-week histology cohorts) will be included in the Intent-to-Treat (ITT) population. All Baseline characteristics and demographic data will be summarized using the ITT population. The ITT population will be based on randomized treatment if this differs from actual treatment received.

#### **12.4.2 All Patients Population**

For the open-label single-blind cohort, all enrolled subjects will be included in the All Patients population. All Baseline characteristics and demographic data for the open-label single-blind cohort will be summarized using the All Patients population. The All Patients population will be based on enrolled treatment if this differs from actual treatment received.

#### **12.4.3 Safety Population**

All randomized/enrolled subjects who receive at least one dose (full or partial) of study drug and have at least one post-dose safety evaluation will be included in the Safety population. All safety endpoints will be summarized using the Safety population and will be based on actual treatment received if this differs from the randomized/enrolled treatment.

#### **12.4.4 Efficacy Population**

All randomized/enrolled subjects who receive at least one dose (full or partial) of study drug and have at least one valid, non-missing post-dose efficacy/PD parameter value will be included in the Efficacy population. All efficacy and PD endpoints will be summarized and analyzed using the Efficacy population. This will be the main population for the analysis of efficacy and PD endpoints. The Efficacy population will be based on randomized/enrolled treatment if this differs from actual treatment received.

#### **12.4.5 Per Protocol Population**

The Per Protocol (PP) population will constitute a subset of the Efficacy population and will include subjects that have at least one valid, non-missing post-dose liver fat content measurement. Subjects in the Efficacy population who deviate from the conduct of the study or have an AE deemed by the Medical Monitor to be impactful on the primary endpoint will be excluded from the PP population. This will be the secondary population for the analysis of efficacy and PD endpoints. The PP population will be based on actual treatment received if it differs from that to which the patient was randomized/enrolled.

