Statistical Methods:	
All patients who receive any amount of study drug will be included in the analyses, including those who withdraw prematurely from the study. Patients will be summarized within five analysis populations:
 
 
• Intent-to-treat (ITT) population: all randomized patients (for the double-blind and placebo-controlled 24-week histology cohorts)
 
• All Patients population: all enrolled patients (single-blind cohort only)
 
• Safety population: all randomized/enrolled patients who receive at least one dose (full or partial) and have at least one post-dose safety evaluation
 
• Efficacy population: all randomized/enrolled patients who receive at least one dose (full or partial) of study drug and have at least one valid, non-missing post-dose efficacy/PD parameter value
 
• Per Protocol (PP) population: subset of patients in the Efficacy population; will include patients who have at least one valid, non-missing post-dose liver fat content measurement and excludes those patients who deviate from the conduct of the study or have an AE deemed by the medical monitor to be impactful on the primary endpoint
 
• Liver histology population: subset of patients in the Efficacy population; will include patients who have at least one valid, non-missing Baseline and EOT biopsy and excludes those patients who deviate from the conduct of the study or have an AE deemed by the medical monitor to be impactful on the primary endpoint
 
• PK population: all randomized/enrolled patients who receive at least one dose (full or partial) of drug, with a pre-dose (Baseline) blood draw, and at least one qualified (above the limit of quantification) post-dose sample
 
 
The patient disposition will be presented by randomized treatment group for the double-blind and placebo-controlled 24-week histology cohorts and by enrolled treatment group for the single-blind cohort. The reasons for discontinuation will also be summarized. Treatment exposure will be summarized as extent of exposure to the study drug. Measures of extent of exposure will include the total number of doses per patient and compliance. Treatment exposure will be summarized using the Safety population by actual treatment group. Demographic and Baseline characteristics will be descriptively summarized by treatment group. Patient disposition, demographic, and Baseline characteristics will be summarized using the ITT population for the double-blind and placebo-controlled 24-week histology cohorts and using the All Patients population for the single-blind cohort.

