For the double-blind cohort, dose reductions will be allowed on a case by case basis for subjects receiving 6 mg or matched 6 mg placebo for safety or tolerability, but must be approved by the Medical Monitor. If approved, the subject will be decreased to 3 mg or the matched 3 mg placebo to be aligned with whether they were initially receiving active drug or placebo prior to the dose reduction. Subjects receiving 3 mg or matched 3 mg placebo will not be allowed to dose-reduce during the study period.

For the open-label single-blind cohort, no dose reductions will be allowed.

For the placebo-controlled 24-week histology cohort **no dose reductions** will be allowed. Additionally, ALT, AST, and all lipid laboratory results are blinded starting with Week 2 onward. The Medical Monitor will be reviewing and monitoring all laboratory results and if any of the liver related testing parameters are observed, investigators will be notified immediately to discuss further evaluation.

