### **9.6.3 Week 2 Procedures**

Subjects will report to clinic fasted and not dosed with NGM282. The following procedures will be performed:

Pre-dose:

- Measure vital signs (including temperature, respiratory rate, and seated blood pressure and pulse).

- Obtain blood for 10-hour fasted clinical laboratory samples (if not fasted, chemistries and lipid panel will need to be retested)
  - Results are blinded for ALT, AST, Total Cholesterol, LDL, HDL and triglycerides
- Record concomitant medications.
- Record new and/or changes to AEs.

In-clinic dosing and dispensing:

- Collect old NGM282 study-drug kit/diary and conduct reconciliation.
- Dispense new NGM282 study-drug kits (2) and diary.
- Dispense rosuvastatin medication/diary
- Oversee subject's NGM282 study-drug self-administration (from new kit).
- Perform LISSA evaluation.

Before clinic discharge:

- Remind subject to bring study drug kits/diary and to not self-inject NGM282 at home on clinic visit days.
- Schedule Week 4 visit and remind subject for home dosing to administer NGM282 or placebo as close as possible to the same time each day

Lipid-Lowering Therapy Assessment:

- NGM Medical Monitor/designee will evaluate LDL-C level as outlined in [Section 10.4](#) and inform site to:
  - Start or not start rosuvastatin therapy
  - Continue with current therapy
  - Switch to rosuvastatin therapy
- The site will then contact the subject with further instructions

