### **9.9.4 Clinical Laboratory Evaluations**

Clinical laboratory evaluations including chemistry (fasted at least 10 hours), CBC, and UA will be collected as outlined in the respective Schedules of Study Procedures (double-blind, [Table 2](#); open-label, [Table 3](#); placebo-controlled 24-week histology, [Table 4](#)).

Laboratory assessments of fasted lipid panel (total cholesterol, LDL, HDL, and TG), lipoprotein particles, HbA1c, insulin, HOMA-IR, and FFAs will be performed as outlined in the respective Schedules of Study Procedures (double-blind, [Table 2](#); open-label, [Table 3](#); placebo-controlled 24-week histology, [Table 4](#)). For the placebo-controlled 24 week histology, test results will be monitored by the sponsor's medical monitor/designee, but are blinded to the site and subject for ALT, AST, Total Cholesterol, LDL, HDL and triglycerides for Week 2 – Week 30 sample collections. LDL-direct may be used if LDL-C was not able to be analyzed.

Laboratory assessments for C4 and serum bile acids will be performed as outlined in the respective Schedules of Study Procedures (double-blind, [Table 2](#); open-label, [Table 3](#); placebo-controlled 24-week histology, [Table 4](#)).

Laboratory assessments for changes in bile-mediated absorption as measured by vitamin D and INR will be performed as outlined in the respective Schedules of Study Procedures (double-blind, [Table 2](#); open-label, [Table 3](#); placebo-controlled 24-week histology, [Table 4](#)).

Cytokines (IL-6, and TGF- $\beta$ ) and hs-CRP will be assessed as outlined in the respective Schedules of Study Procedures (double-blind, [Table 2](#); open-label, [Table 3](#)).

Hepatitis screen and HIV antibody screen will be performed at Screening.

A urine screen for drugs of abuse will be performed at Screening.

A stool sample will be collected at Day 1 and Week 12 in only the double-blind and open-label single-blind cohorts. Stool samples will be analyzed for microbiome (bacterial composition) and fecal fat content (double-blind, [Table 2](#); open-label, [Table 3](#)).

A serum qualitative pregnancy test (all female patients of child bearing potential) will be performed at Screening and Week 24/EOT and Week 30/EOS. A urine pregnancy test (all female patients of child bearing potential) will be performed at Day 1 (pre-dose).

AFP will be measured at Screening.

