#### **12.4.6 Liver Histology Population**

The liver histology population will constitute a subset of patients in the Efficacy population and will include patients who have at least one valid, non-missing Baseline and EOT liver biopsy. Subjects in the Efficacy population who deviate from the conduct of the study or have an AE deemed by the Medical Monitor to be impactful on the primary endpoint will be excluded from the PP population. This will be the secondary population for the analysis of efficacy and PD endpoints. The PP population will be based on actual treatment received if it differs from that to which the patient was randomized/enrolled.

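### In the 24-week cohort, Per Protocol exclusion (and, in the synopsis only, Liver Histology exclusion) rests on an AE judgement with no visible criteria or timing, made by a Medical Monitor who sees ALT and lipid results withheld from sites

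*Protocol*

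**What the plan says.** Protocol 12.4.5 builds the Per Protocol set from Efficacy subjects with a post-dose liver fat measurement. It then removes subjects who deviate from study conduct or who "have an AE deemed by the Medical Monitor to be impactful on the primary endpoint". The set is analysed by treatment received and is called the secondary population for efficacy.

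The Liver Histology set is defined twice. The synopsis (Statistical Methods) takes patients with "at least one valid, non-missing Baseline and EOT biopsy and excludes those patients who deviate from the conduct of the study", and continues with the same Medical Monitor AE ground. Protocol 12.4.6 also asks for paired biopsies, but its exclusion sentence says that the affected subjects "will be excluded from the PP population". Its treatment-assignment sentence also names the Per Protocol population.

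On laboratory access in the 24-week cohort, Protocol 8.2 states: "The Medical Monitor will be reviewing and monitoring all laboratory results". Section 9.9.4 says that results are monitored by the sponsor's medical monitor or designee, "but are blinded to the site and subject for ALT, AST, Total Cholesterol, LDL, HDL and triglycerides", from Week 2 to Week 30. Sections 9.6.3, 9.6.4, 9.6.6 and 9.6.7 have the Medical Monitor or designee evaluate LDL-C and tell the site how lipid therapy should proceed.

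**The concern.** An adverse event occurs after randomisation and may be caused by the drug. Excluding subjects because one person thinks the event affected the primary endpoint makes set membership depend on a subjective, outcome-linked judgement. That is tolerable if the person deciding cannot tell the arms apart and the rules are fixed beforehand. Here neither condition is visible.

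Protocol 5.5 says that NGM282 raises total cholesterol and LDL-C. Section 5.7 reports ALT falls by Week 2 in the double-blind cohort (3 and 6 mg), and section 5.4 reports ALT changes at 1 mg, this cohort's dose, comparable to those at 3 mg in the first 10 subjects. Someone who follows these results for 24 weeks may form a view of the arm. GI symptoms and injection-site reactions are reported with the drug (sections 5.1.3 and 5.4), so AE exclusions could fall more on NGM282 and remove subjects who tolerated it poorly.

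At stake is the credibility of the Per Protocol repeat of the primary analysis (Protocol 12.9.2) and of the secondary analyses (SAP 8.2). The latter include histologic response, the outcome on which this cohort was sized. For the Liver Histology set there is a further problem: the primary endpoint is liver fat, so the synopsis clause would filter a biopsy set on a liver-fat criterion.

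**Working it through.** **1. The exclusion rule, place by place**

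- Protocol 12.4.5 (Per Protocol): the AE ground is explicit, with no event list, threshold, timing or blinding condition.
- Synopsis (Liver Histology): the same AE ground is explicit.
- Protocol 12.4.6 (Liver Histology): the sentence is repeated, but the exclusion is from the Per Protocol set. Read literally, the body text puts no AE exclusion on Liver Histology and does not say by which treatment it is analysed.
- SAP 5.4 and 5.5 (both sets): redacted, content unknown.
- SAP 5.6: pre-lock review and predefined criteria, for protocol deviations only. AE exclusions are not mentioned.

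**2. Who knows what in the 24-week cohort**

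- Site and subject: no ALT, AST or lipid results from Week 2.
- Medical Monitor: all laboratory results.
- Formal blinding (Protocol 12.2): Sponsor, sites and subjects. Sections 8.3 and 10.4.2 refer to the Sponsor's Medical Monitor, so this person falls within the blinded Sponsor. The double-blind cohort text (section 7) names the Medical Monitor as blinded; the 24-week text does not do so separately.

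The Medical Monitor is therefore blinded to assignment but not to data that may indicate it. The withheld-results mechanism belongs to this cohort, although the clause in 12.4.5 covers all cohorts.

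**3. Which analyses depend on these sets**

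- Main primary and secondary analyses: Efficacy population, no AE exclusion (Protocol 12.4.4, 12.9.2, 12.9.3; SAP 5.3, 8.2).
- Per Protocol: repeat analyses only.
- Liver Histology: the visible SAP text assigns it no analysis.

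**4. The plan's own sample size**

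Inputs (Protocol 12.1, SAP 3.5): 50% versus 15% response, 80% power, two-sided 0.05, 2:1 allocation, 15% dropout. The formula uses pooled variance without continuity correction.

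- p̄ = (0.15 + 2 × 0.50)/3 = 0.3833
- n(placebo) = [1.960·√(p̄(1−p̄)(1 + 1/2)) + 0.842·√(0.15·0.85 + 0.50·0.50/2)]² / 0.35² = (1.167 + 0.423)²/0.1225 = 20.6, so 21; NGM282 42
- Dropout: 21/0.85 = 24.7, so 25; 42/0.85 = 49.4, so 50

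The stated 50 + 25 is reproduced, with 42 versus 21 evaluable and power of 80.8%.

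**5. Illustration of sensitivity**

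Assumptions, not document figures: 42 versus 21; the same true response of 15% to 20% in both arms; uncorrected chi-square at 0.05; exclusions that always track arm and outcome. The documents do not say that the Medical Monitor sees MRI or biopsy results, so perfect tracking of outcome is a worst case. The method is to sum the exact binomial probabilities of all tables that are significant in favour of NGM282 after exclusion.

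| Excluded | False result favouring drug |
|---|---|
| None | 2.0–2.1% |
| 2 NGM282 non-responders | 2.1–2.6% |
| 4 NGM282 non-responders | 2.7–3.3% |
| 1 placebo responder | 6.0–6.8% |
| 4 NGM282 non-responders and 1 placebo responder | 9.0–9.6% |

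The tolerability route described above corresponds to the second and third rows. The last two need a placebo responder to be removed, which nothing in the documents makes especially likely.

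A hypothetical borderline case: 18/42 versus 4/21 gives p = 0.062, and dropping two NGM282 non-responders (18/40 versus 4/21) gives p = 0.045. The count was chosen to sit at the boundary. With 17 responders, 17/40 gives 0.067; with 19, 19/42 is already 0.042. Between 14 and 23 NGM282 responders, only 18 behaves this way.

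**The case against.** Much can be said for the plan.

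- The SAP sections that define both sets are redacted and may already drop the AE clause or require blinded, pre-lock decisions. This stands: the point is about the visible text, and the fix must be conditional on it.
- The Sponsor is formally blinded, and no visible text gives the Medical Monitor assignments. This stands. A reader might infer that the Medical Monitor is unblinded or selects subjects by arm. The documents support only that the withheld results could allow inference, to an unknown degree. They give no LDL-C or ALT separation between 1 mg and placebo.
- The main analyses use the Efficacy population. This also stands. A reader might infer that the cohort's principal result is at risk; it is not.
- A reader might say that both sets carry the clause. Only the synopsis applies it to Liver Histology; 12.4.6 directs the exclusion at the Per Protocol set.
- Section 5.4 reports fewer injection-site reactions and less persistent GI symptoms at 1 mg than at 3 mg, and subjects who stop early without an EOT biopsy are outside the Liver Histology set in any case. Both facts reduce the number of exclusions that the clause could drive.
- Objective substitutes such as a compliance threshold or a Week 24 MRI are also post-randomisation. That is true: they remove discretion, not selection.

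What remains is a discretionary, outcome-linked exclusion with no visible rule, made by someone who sees possibly revealing data.

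**Conclusion.** The concern holds for the Per Protocol set in the 24-week cohort. For the Liver Histology set it holds only if the synopsis wording governs, and the conflict between the synopsis and 12.4.6 is a defect in its own right. The consequence is possible bias in supportive analyses; the Efficacy-population analyses stand whatever is decided.

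The size of any bias cannot be computed, because the documents give neither an expected number of AE exclusions nor the laboratory separation between arms at 1 mg. Under the stated worst-case assumptions, two to four selective NGM282 exclusions move the false-result rate favouring the drug from about 2% to between 2.1% and 3.3%. That is modest, but it can be avoided by wording alone. The conclusion assumes that redacted SAP 5.4 and 5.5 do not already supply the missing rule.

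**What to change.** 1. In Protocol 12.4.5 and the synopsis, delete the AE clause from the Per Protocol definition. Alternatively, replace it with objective criteria fixed in advance and applied before database lock by someone without access to the withheld ALT, AST and lipid results. Criteria that are themselves post-randomisation, such as compliance or presence of the Week 24 MRI, should be acknowledged as such and the set kept supportive.
2. Reconcile the synopsis with Protocol 12.4.6, correcting the exclusion and treatment-assignment sentences that name the Per Protocol population. Define Liver Histology as Efficacy subjects with valid baseline and EOT biopsies, analysed as randomised, with no exclusion tied to liver fat.
3. If SAP 5.4 and 5.5 already say this, align the protocol to them; otherwise amend both documents together.

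The cost is wording, plus naming a reviewer if a judgement is kept. Sample size does not change. The downside is that a few subjects whose treatment was affected by an AE stay in the sets.

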#### **12.4.6 Liver Histology Population**

The liver histology population will constitute a subset of patients in the Efficacy population and will include patients who have at least one valid, non-missing Baseline and EOT liver biopsy. Subjects in the Efficacy population who deviate from the conduct of the study or have an AE deemed by the Medical Monitor to be impactful on the primary endpoint will be excluded from the PP population. This will be the secondary population for the analysis of efficacy and PD endpoints. The PP population will be based on actual treatment received if it differs from that to which the patient was randomized/enrolled.

#### **12.4.7 Pharmacokinetic Population**

All randomized/enrolled subjects who receive at least one dose (full or partial) of drug, with a pre-dose (Baseline) blood draw, and at least one qualified (above the limit of quantification) post-dose sample will be included in the PK population. Subjects with protocol violations will be assessed by the medical monitor for inclusion in the PK population. PK summaries and analyses will be conducted using the PK population. The PK population will be based on actual treatment received if it differs from that to which the patient was randomized/enrolled.

